	To evaluate the safety of combining Deucravacitinib and Enstilar.
	To evaluate the subject quality of life when combining Deucravacitinib and Enstilar.
Study Design	30 adult patients with moderate to severe plaque psoriasis will be given Deucravacitinib 6mg QD for the first 8 weeks of the study.
	At week 8:
	Subjects who do not meet PASI 25 at week 8 will be discontinued from the study as non-responders.
	Subjects who achieve ≥PASI 75 at week 8 will remain enrolled and continue Deucravacitinib 6mg QD monotherapy through week 24.
	Subjects who achieved between PASI 25-74 response will receive 4 weeks of Enstilar (calcipotriene and betamethasone dipropionate) Foam, 0.005%/0.064% applied QD in addition to continuing Deucravacitinib 6mg QD.
	At week 12, (after 4 consecutive weeks of Enstilar), subjects in the PASI 25-74 group, will discontinue Enstilar QD and continue Deucravacitinib as monotherapy through week 24.
	Subjects will return at week 28 for safety follow evaluation.
Study Centers	Psoriasis Treatment Center of New Jersey

PTC09	30August202
Study Population	Adult male and female subjects with moderate to severe chronic plaque psoriasis
Main Inclusion Criteria	Subjects must meet the following criteria to be enrolled in this study: 1.Male or female adult ≥ 18 years of age; 2. Diagnosis of chronic plaque-type psoriasis 3. Moderate to severe plaque type psoriasis as defined at baseline by: • BSA affected by plaque-type psoriasis of 10% or greater • PGA score of 3 or greater • PASI ≥ 12. 4. Able and willing to give written informed consent prior to performance of any study-related procedures Must be in general good health (except for disease under study) as judged by the Investigator, based on medical history, physical examination, clinical laboratories, and urinalysis.
Main Exclusion Criteria	Subjects who meet any of the following criteria will be excluded from participation in this study: 1. Other than psoriasis, any clinically significant (as determined by the investigator) cardiac, endocrinologic, pulmonary, neurologic, psychiatric, hepatic, renal, hematologic, immunologic disease, or other major disease that is uncontrolled. 2. Forms of psoriasis other than chronic plaque-type (e.g., Pustular erythrodermic and/or guttate psoriasis) or drug induced psoriasis 3. Use of oral systemic medications or PUVA phototherapy for the treatment of psoriasis within 4 weeks (includes, but not limited to, oral corticosteroids, methotrexate, acitretin and cyclosporine). 4. Prior use of biologics within the following periods: • Etanercept – 4 weeks • Adalimumab or certolizumab pegol – 8 weeks • IL-17 antagonists – 16 weeks • Ustekinumab or IL-23 pathway inhibitors – 24 weeks • Other biologics - 5 half-lives 5. Patient used topical therapies or UVB phototherapy to treat psoriasis within 2 weeks of the Baseline Visit (includes, but not limited to, topical corticosteroids, vitamin D analogs, or retinoids).

Study Drug Dosage and Administration	All subjects will receive Deucravacitinib 6mg daily at week 0 (baseline) through week 8. At week 8, patients who achieved between PASI 25-74 response will receive 4 weeks of Enstilar (calcipotriene and betamethasone dipropionate) Foam, 0.005%/0.064% once daily in addition to continuing Deucravacitinib 6mg daily. At week 12 (after 4 consecutive weeks of Enstilar therapy), Enstilar will be discontinued and patients will continue Deucravacitinib 6mg daily as monotherapy through week 24. Patients who achieve ≥PASI 75 at week 8 will remain enrolled on Deucravacitinib 6mg QD monotherapy through week 24.
Study Endpoints	Primary Endpoint: Proportion of subjects achieving PASI 75 at week 12 for patients in the Deucravacitinib + Enstilar combination arm. Secondary Endpoints: Proportion of subjects achieving PASI 25-74 at week 8. PASI, PGA, BSA, PGAxBSA and DLQI improvement at weeks 8, 12, 16, 20, 24. PASI 75 at weeks 16 and 24 Serious Adverse Events (SAE's)
Study Duration	28 weeks

2 ETHICS AND REGULATORY OBLIGATIONS

2.1 Institutional Review Board (IRB)

Written IRB approval of this protocol must be obtained before the study is initiated. Compliance with Title 21 of the US Code of Federal Regulations (CFR), Part 56, is required in order to protect the rights and welfare of human subjects involved in this study.

2.2 Ethical Conduct of the Study

The study will be conducted in accordance with the ethical principles that have their origins in the Declaration of Helsinki and its amendments. In addition, the study will be performed in compliance with Good Clinical Practices (GCP), including the archiving of essential documents.

2.3 Subject Information and Consent

The Informed Consent Form will be reviewed and approved by the IRB. The purpose, duration and possible risks and benefits will be explained to each potential subject. Consent in writing must be obtained from the subject before enrollment into the study. Consents will be signed and dated as required by Title 21 of CFR, Part 50. The consent will also comply with the requirements of the Health Insurance Portability and Accountability Act (HIPAA). The original, signed Informed Consent Form will be retained by the Investigator. A signed copy of the Informed Consent Form will be given to the subject. Each subject will be assigned a subject number that will be used in lieu of the subject's name on further research documentation.

3 INTRODUCTION

3.1 Overview of Psoriasis

Psoriasis is a chronic immunological disease characterized by infiltration of the skin with activated T cells and by abnormal keratinocyte proliferation and differentiation, resulting in marked inflammation and thickening of the epidermis. Psoriasis affects 1-3% of the world population, making it one of the most prevalent inflammatory immunological diseases.¹ There are several clinical subtypes of psoriasis: plaque, guttate, erythrodermic, inverse, and pustular. Plaque psoriasis is the most common type of psoriasis affecting 75-80% of psoriasis sufferers.² It presents as raised silvery scale, which can cover large areas, with underlying erythema, itching, and discomfort

7

3.2 Rationale for Treating Plaque Psoriasis with Deucravacitinib + Enstilar

Deucravacitinib is an investigational TYK2 inhibitor that has been tested for the treatment of moderate-to-severe psoriasis. Combination regimens that utilize a systemic agent with light therapy and/or a topical agent are becoming the standard of care in the United States³ and Europe⁴, confirming the observation of Lebwohl et al⁵ in 2004, that the use of two or more therapies to treat patients with moderate to severe psoriasis seems to be the rule rather than the exception. Topical steroids play an in important role in the long-term management of psoriasis and data from the COBRA trial suggests that super potent topical corticosteroids are appropriate and well tolerated for use when added to existing therapeutic regimens i.e. phototherapy, systemic and biologic therapy.⁶ In a similarly designed clinical trial using apremilast with Enstilar add- on therapy it was shown that most week-8 partial apremilast responders achieved PASI 75 at week 12 with combination C/BD topical therapy, and maintained PASI 75 through week 16 with apremilast monotherapy.⁷ This study is being conducted to determine if adding topical Enstilar to deucravacitinib therapy can help patients who received a partial response at week 8 reach PASI 75 by week 12.

4.STUDY OBJECTIVES

The primary objective of this study is to explore the effectiveness of combining deucravacitinib and Enstilar. Secondary objectives will explore the safety and impact on quality of life for subjects receiving deucravacitinib in combination with Enstilar.

5. INVESTIGATIONAL PLAN

5.1 Overall Study Design and Plan

30 subjects affected with plaque psoriasis with body surface area greater than or equal to 10%, and physician's global assessment greater than or equal to 3 and PASI greater than or equal to 12 will receive deucravacitinib 6 mg once daily for 8 weeks. Subjects who do not achieve at least a PASI 25 at week 8 will be discontinued from treatment and study procedures.

At week 8, subjects who have achieved between a PASI 25-74 will receive Enstilar (calcipotriene and betamethasone dipropionate) Foam, 0.005%/0.064% once daily for 4 weeks in addition to continuing deucravacitinib 6mg daily. These subjects will then discontinue Enstilar at week 12 and remain on deucravacitinib monotherapy through week 24.

Subjects who achieve ≥PASI 75 at week 8 will remain enrolled in the study and continue deucravacitinib QD through week 24. These subjects will not receive Enstilar add-on therapy.

All subjects will be asked to return for a safety follow up visit 4 weeks after the last dose of deucravacitinib.

5.2 Study Population Criteria

Males and females ≥ 18 years of age with moderate-to-severe chronic plague psoriasis

5.2.1 Inclusion Criteria

Patients who meet all of the following criteria will be enrolled in the study:

- 1.Male or female adult ≥ 18 years of age
- 2. Diagnosis of chronic plaque-type psoriasis
- 3. Moderate to severe plaque type psoriasis as defined at baseline by:
- Physician's Global Assessment (PGA) score of 3 or greater
- Body Surface Area (BSA) affected by plaque-type psoriasis of 10% or greater
- Psoriasis Area Severity Index of 12 or greater
- 4. Able and willing to give written informed consent prior to performance of any study-related procedures
- 5. Must be in general good health (except for disease under study) as judged by the Investigator, based on medical history, physical examination, clinical laboratories, and urinalysis. (NOTE: The definition of good health means a subject does not have uncontrolled significant co-morbid conditions).
- 6.Females of childbearing potential (FCBP) must have a negative serum pregnancy test at Screening and negative urine pregnancy test at Baseline. FCBP who engage in activity in which conception is possible must use one of the approved contraceptive options: hormonal contraception; intrauterine device (IUD); tubal ligation; or partner's vasectomy; Male or female condom diaphragm with spermicide, cervical cap with spermicide, or contraceptive sponge with spermicide.

5.2.2 Exclusion Criteria

Patients will NOT be enrolled in this study if they meet any of the following criteria:

- 1. Other than psoriasis, any clinically significant (as determined by the Investigator) cardiac, endocrinologic, pulmonary, neurologic, psychiatric, hepatic, renal, hematologic, immunologic disease, or other major disease that is currently uncontrolled.
- 2. Pregnant or breast feeding, or considering becoming pregnant during the study.
- 3. Subjects with a current malignancy or prior malignancy within the last 5 years (excluding successfully treated basal cell carcinoma, squamous cell carcinoma of the skin or carcinoma in situ of the cervix that has been adequately treated).
- 4. Subjects with diagnosis of active tuberculosis or untreated latent tuberculosis. Subjects will be eligible if they have previously received adequate treatment for latent TB or initiate 4 weeks of prophylactic LTBI treatment prior to

Baseline visit and agree to complete treatment course as prescribed.

- 5. History of or positive screening serology for Hepatitis B surface antigen (HBsAg); Hepatitis C virus antibody and/or HIV.
- 6. Use of any investigational drug within 4 weeks prior to randomization, or within 5 pharmacokinetic/pharmacodynamic half-lives, if known (whichever is longer).
- 7. Prior treatment with deucravacitinib.
- 8. Active forms of psoriasis other than chronic plaque-type (e.g., pustular erythrodermic and/or guttate psoriasis) or drug induced psoriasis
- 9. Prior use of biologics within the following periods:
 - Etanercept 4 weeks
 - Adalimumab or certolizumab pegol 8 weeks
 - IL-17 antagonists 16 weeks
 - Ustekinumab or IL-23 pathway inhibitors 24 weeks
 - Other biologics 5 half-lives
- 10. Use of oral systemic medications or PUVA for the treatment of psoriasis within 4 weeks (includes, but not limited to, oral corticosteroids, methotrexate, acitretin and cyclosporine).
- 11. Patient used topical therapies within 2 weeks of the Baseline Visit (includes, but not limited to, topical corticosteroids, vitamin D analogs, or retinoids).
- 12. Patient received UVB phototherapy within 2 weeks of Baseline.
- Patient has a known hypersensitivity to the excipients of deucravacitinib or Enstilar.
- 14. Any condition which would place the subject at unacceptable risk if he/she were to participate in the study.

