5.6.3 Demographics and Medical History

The following information will be obtained for each subject during screening: date of birth, sex, race/ ethnic origin, relevant medical and surgical history, including year of diagnosis of plaque psoriasis, and current and previous anti-psoriasis treatments for the last 6 months. All current therapies for other medical conditions will be documented. Medical history will be reviewed and updated at the Baseline Visit to ensure that the patient remains eligible to participate in the study.

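### The systemic washout covers only oral drugs, so an injected corticosteroid given for psoriasis just before baseline is not excluded, and its carry-over could bias PASI response

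*Combined protocol and SAP*

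**What the plan says.** Section 5.2.2, item 10, excludes "Use of oral systemic medications or PUVA for the treatment of psoriasis within 4 weeks (includes, but not limited to, oral corticosteroids, methotrexate, acitretin and", and the open-ended list of examples closes with cyclosporine. Synopsis exclusion 3 carries the same limit: "Use of oral systemic medications or PUVA phototherapy for the treatment of psoriasis within 4 weeks". Neither place says which visit the 4 weeks are counted back from.

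The neighbouring washouts cover other classes. Item 6 deals with investigational drugs and item 12 with UVB. Item 9 begins "Prior use of biologics within the following periods" and lists biologics only. Item 11 reads "Patient used topical therapies within 2 weeks of the Baseline Visit"; items 11 and 12 both name Baseline as the anchor. Item 14 is a general clause on risk: "Any condition which would place the subject at unacceptable risk if he/she were to participate in the study".

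Under sections 5.1 and 5.6, week-8 PASI response sends a subject one of three ways: discontinued below PASI 25, given add-on Enstilar at PASI 25–74, or kept on monotherapy at PASI 75 or above. The synopsis defines the primary endpoint as the proportion with PASI 75 at week 12 in the add-on group. Section 8.2 describes a pilot of 30 patients without formal hypothesis testing.

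**The concern.** Item 10 is limited by route twice: in its head term, and again where corticosteroids are named. An open-ended list of examples does not widen a class already restricted to oral drugs. A corticosteroid injected for psoriasis a few days before baseline is thus outside the rule, although a topical one needs 2 weeks off and an oral one 4 weeks. That ordering is unlikely to be intended.

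One PASI-based measure decides who is discontinued, who enters the primary-endpoint cohort, and who counts as a success in it. Without a concurrent control, the effect of a pre-study injection cannot be separated from the effect of study treatment. An injection that has already lowered baseline PASI and then fades makes improvement look smaller. One that acts mainly after baseline makes it look larger.

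**Working it through.** **Does another provision close the gap?**

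| Provision | Reaches an injected corticosteroid given for psoriasis before baseline? |
|---|---|
| 5.2.2 items 6, 9, 11, 12 | No: investigational drugs, biologics, topicals, UVB |
| 5.2.2 item 14 | No: risk, not washout |
| 5.5.4 | No: lists permitted therapy; sets no bar on residual effect of an earlier drug |
| 5.6.2 | No: asks for changes needed to meet the listed criteria; adds none |
| 5.6.3 | Records "current and previous anti-psoriasis treatments for the last 6 months", but recording excludes no one |
| 5.6.12 item 5 | No: therapy begun on study |

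For methotrexate the text supports two readings. The drug is named without a route, which suggests any route; it stands in a list illustrating oral drugs, which suggests oral only.

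**How large could the effect be?** The plan has no figure of its own to reproduce. PASI 25 and PASI 75 are taken as percent improvement from baseline. Assumptions not in the documents: a 10–30% effect of the injected drug on PASI, multiplicative effects, and an add-on cohort of 10–20 subjects.

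*A. Baseline lowered by a fraction s, effect gone by the later visit.* With true improvement p, observed improvement = 1 − (1 − p)/(1 − s).

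- At p = 75%: 1 − 0.25/0.9 = 72.2%; 1 − 0.25/0.8 = 68.8%; 1 − 0.25/0.7 = 64.3%.
- Who falls below PASI 75: the observed value reaches 75% only if p ≥ 1 − 0.25(1 − s), which is 77.5%, 80% or 82.5%. So only true improvements from 75% to just under those values cross. A true 85% at s = 30% still reads 1 − 0.15/0.7 = 78.6%.
- Who falls below PASI 25: the same step gives p < 1 − 0.75(1 − s), which is 32.5%, 40% or 47.5%. For example, an unsuppressed PASI of 20 and a week-8 PASI of 14 is a true 30%; at s = 10% it reads 1 − 14/18 = 22.2%, and the subject is discontinued.
- The entry floor of PASI 12 (5.2.1) limits this only partly. An unsuppressed 20 becomes 18, 16 or 14, all eligible; an unsuppressed 16 at s = 30% becomes 11.2 and is excluded.

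*B. Baseline unaffected, later PASI lowered by a fraction r.* Observed improvement = 1 − (1 − p)(1 − r). At r = 10%, a true 72.5% reads 1 − 0.275 × 0.9 = 75.25%, so at week 8 the subject leaves the primary cohort; a true 20% reads 1 − 0.80 × 0.9 = 28%, so the subject enters it. This needs the drug still to be acting at week 8, or at week 12 to alter the endpoint directly.

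*Effect on the primary proportion.* A crossing of the 75% cut at week 12 changes it by 1/n: 10.0, 6.7 or 5.0 points for n = 10, 15 or 20. A week-8 crossing instead changes who is in the cohort: with x successes among n, adding one subject turns x/n into (x + 1)/(n + 1) or x/(n + 1), so 1/n is not the right figure there. No crossing, no change.

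**The case against.** The strongest reply is practical. This is one center, the sponsor is also the principal investigator, and section 5.3 gives the investigator charge of recruitment, so there is no variation between sites in reading item 10. Six months of psoriasis treatment are recorded and the history is reviewed at Baseline, so a recent injection should be seen. The severity floors remove heavily suppressed candidates. The study is a pilot reported with summary statistics, so no error rate or power figure changes. All of this stands, and it lowers the severity. It does not close the gap: the investigator may decline such a subject, but no stated rule requires it.

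Three stronger readings are tempting and should be resisted.

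- A reader might infer that injected methotrexate is plainly allowed. The text is ambiguous on it; only the injected corticosteroid is clearly outside the rule.
- A reader might infer that carry-over does shift the cohorts and the endpoint. The documents do not say how many candidates receive such injections, or how strongly or for how long they act, and mechanisms A and B pull in opposite directions. Mechanism B further requires an effect lasting to week 8 or 12, for which the documents offer no support.
- A reader might infer that every exposed subject moves the primary result by 5–10 points. Only a subject who crosses the 75% cut at week 12 does so.

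**Conclusion.** The gap in the eligibility rule is real and appears in both places where the rule is stated. It admits a subject whose PASI response may partly reflect an earlier drug, in an uncontrolled study where that response sets discontinuation, cohort and primary endpoint. What the documents support is a possible bias of unknown sign and size. The 5–10 point figure applies per subject crossing the cut at week 12, and rests on the assumed cohort of 20–10; under the assumed 10–30% baseline suppression, such crossings are confined to the narrow bands shown above. Severity is minor to moderate: nothing inferential depends on it, but the estimated proportion is the study's main result and the correction is cheap.

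**What to change.** In section 5.2.2 item 10 and synopsis exclusion 3, replace the oral-only head term with *systemic non-biologic medications by any route*, and replace the oral-only corticosteroid example with *systemic corticosteroids*. This also settles methotrexate. In the same edit, count the window back from the Baseline Visit, as items 11 and 12 do. The investigator should confirm the window for injected forms; this review proposes none.

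No new data item is needed, because section 5.6.3 already collects prior psoriasis treatment. If anyone has already been enrolled after a recent non-oral systemic treatment, a listing of those subjects, with the primary proportion shown with and without them, would reveal any effect. The cost is a few words in two places, and a recently injected candidate may have to wait or be excluded.

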5.3 Source of Subjects and Recruitment Methods

The Investigator will manage the recruitment of subjects upon approval of the study by the Institutional Review Board. Subjects may be recruited from internal patient lists and outside IRB approved advertisements.

5.4 Subject Enrollment and Treatment Assignment

30 subjects of either gender with moderate-to severe plaque psoriasis will receive deucravacitinib 6mg QD for 8 weeks. Participation beyond week 8 will be determinate of subject response according to the study design.

5.5 STUDY TREATMENT

5.5.1 Deucravacitinib Treatment

5.5.2 Deucravacitinib Description

Deucravacitinib is manufactured by Bristol Myers Squibb. Tyrosine kinase 2 (TYK2) is associated with specific cytokine receptors and catalyzes the phosphorylation of signal transducer and activator of transcription (STAT) proteins downstream of these receptors including the receptors for p40-containing cytokines, interleukin (IL)-12, and IL-23, as well as the interferon-α and interferon-β. Type I interferon [IFN]) receptor. TYK2 activity results in the activation of STAT-dependent transcription and functional responses specific for these receptors. Deucravacitinib is a stable deuterium-labeled compound (where deuterium is a stable, nonradioactive isotope of hydrogen) and a potent, highly selective small molecule inhibitor of TYK2. Deucravacitinib has a unique mode of binding that provides the high selectivity over the other members of the JAK family of non-receptor tyrosine kinases.⁸ Selective inhibition of TYK2 with the oral agent deucravacitinib at doses of 3 mg daily and higher resulted in greater clearing of psoriasis than did placebo.⁹

5.5.2.1 Deucravacitinib Dosing Schedule

Deucravacitinib 6mg tablets will be supplied by Bristol Myers Squibb and administered once daily (recommended in the mornings). It is recommended the first dose of IP will be taken in the clinic at the baseline visit.

5.5.2.2 Deucravacitinib Dispensing

Subjects will return all unused deucravacitinib tablets to the study site. Site personnel will keep a record of deucravacitinib dispensed to and returned by each subject and note any missed doses.

5.5.2.3 Deucravacitinib Dosage Adjustments

If an SAE or an adverse event that is thought to be related to deucravacitinib and is not alleviated by symptomatic intervention, deucravacitinib will be discontinued. Subjects who permanently discontinue deucravacitinib therapy under this protocol should receive standard care of psoriasis treatment as prescribed by their physician.

5.5.3 ENSTILAR (calcipotriene and betamethasone dipropionate) Foam, 0.005%/0.064%

5.5.3.1 Enstilar Description

Enstilar foam is a combination of calcipotriene, a vitamin D analog, and betamethasone dipropionate, a corticosteroid, indicated for the topical treatment of plaque psoriasis in patients 18 years of age and older. Each gram of Enstilar Foam contains 52.2 mcg calcipotriene hydrate (equivalent to 50 mcg of calcipotriene) and 0.643 mg of betamethasone dipropionate (equivalent to 0.5 mg of betamethasone).

